10.1.1.4 Causality Assessment

The investigator determines the causality of all AEs to the study drug using medical judgment and considering all relevant factors such as (but not limited to) the underlying study indication, coexisting disease, concomitant medication, relevant history, pattern of the AE, temporal relationship to the study drug, and de-challenge or re-challenge. The causality assessment of the AE/SAE is to be made as follows.

Related to study drug (possibly, probably, or definitely related)

Based on medical judgment, there is at least a reasonable possibility that the study drug caused the event; one or more of the following criteria apply:

- The event follows a reasonable temporal sequence from administration of study drug
- The event could not be reasonably attributed to the known characteristics of the patient's clinical state, environmental or toxic factors, or other modes of therapy administered to the patient
- The event follows a known pattern of response to study drug
- The event disappears or decreases on cessation or reduction in dose of the study drug. (It should be noted that in some situations an AE will not disappear or decrease in intensity upon discontinuation of study drug despite other clear indications of relatedness)
- The event reappears or worsens when the study drug is re-administered

Unrelated to study drug (unlikely or unrelated)

Based on medical judgment there is no reasonable possibility that the study drug caused the event; one or more of the following criteria apply:

- The event does not follow a reasonable temporal sequence from administration of study drug
- The event could be reasonably attributed to the known characteristics of the patient's clinical state, concurrent illness, environment or toxic factors, or other modes of therapy administered to the patient
- The event does not follow a known pattern of response to study drug
- The event does not disappear or decrease on cessation or reduction in dose of the study drug, and it does not reappear or worsen when the study drug is re-administered

10.1.2 Recording of Adverse Events

It is the investigator's responsibility to assess whether each untoward event is a clinically significant worsening from baseline, thereby considered an AE. For all AEs, the severity, seriousness, and causality to study drug for each AE as outlined in [Section 10.1.1](#) will be assessed and recorded in the eCRF.

All serious and non-serious AEs are collected once the caregiver/patient has signed the ICF and until the post-treatment follow-up (Visit 12), 28 days after the last dose of study drug. Collection of all serious and non-serious AEs will continue for the optional extension period.

Any AEs or SAEs that are unresolved at the patient's last AE assessment in the study are followed up by the investigator until resolution or stabilization up to the database lock and

recorded in the eCRF. Albireo retains the right to request additional information for any patient with ongoing AE(s) or SAE(s) at the end of the study.

TEAEs that are ongoing at time of discontinuation will be followed up until week 72 by telephone calls every 3 months. No new AEs will be recorded after the patient has permanently discontinued study drug.

TEAEs are defined as any AE that occurs after dosing (Day 1), including new AEs or the worsening of an event after the first dose.

If there is a clinically significant deterioration of a laboratory value/vital sign or other routine study assessment that is associated with a diagnosis, the clinical diagnosis will be reported as an AE and the associated signs and symptoms will be considered additional information unless the sign or symptom is more severe than expected given the diagnosis. For example, if an investigator diagnoses a study patient with hepatitis during the study period, hepatitis would be considered the AE and the concomitant signs and symptoms of abdominal pain, vomiting, and elevated ALT and AST would not be reported separately unless, in the opinion of the investigator, one of these signs or symptoms is more severe than expected and therefore a separate AE assessment is indicated.

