If a liver biopsy is performed according to the local regulations or standard of care at any time during A4250-008, the biopsy results should be recorded in the electronic case report form (eCRF). If the patient had liver biopsy results collected in study A4250-005 or prior to Week 24 in study A4250-008, the patient will be asked to consent to a follow-up liver biopsy, if allowed per local regulations, at Visit 11, unless 2 prior liver biopsy results have been collected with at least 1 year between biopsies. Liver biopsies will not be performed in Spain.

For those not participating in the optional extension period, Visit 12 will take place 28 days after Visit 11. All patients prematurely withdrawn will have this visit 28 days after the last dose of study drug for AE and other follow-up.

If a patient discontinues prior to Week 72, additional telephone contacts will be made every 3 months after the Follow-up Visit (Visit 12) up to Week 72 to gather whether or not the patient

has had biliary diversion or liver transplantation, and if TEAEs ongoing at the time of discontinuation have resolved. The telephone calls will take place up until 72 weeks even if the patient has biliary diversion or liver transplant.

Details of study assessments are provided in the schedule of assessments ([Table 1](#) and [Table 2](#)).

Figure 1 Study Design

QD: once daily; T: telephone contact; V: study visit; VS: Visit Screening

Note: Visit 1 coincides with Visit 9 of Study A4250-005. Patients who are not tolerating the 120 µg/kg/day dose may be down-titrated to the 40 µg/kg/day dose following a minimum of 1 week of treatment. The patient can return to the higher dose as soon as deemed appropriate.

This figure is only applicable to Cohort 2 up to Protocol Amendment 5. [Figure 2](#) presents the study design for Cohort 2 as of Protocol Amendment 6.

Figure 2 Study Design for Cohort 2 as of Protocol Amendment 6

QD: once daily; T: telephone contact; V: study visit; VS: Visit Screening

Note: As of Protocol Amendment 6, patients entering Cohort 2 will start treatment at 40 µg/kg/day with the possibility to dose escalate to 120 µg/kg/day after 12 weeks if there is no improvement in pruritus based on investigator judgment. The patient can return to the lower dose if the 120 µg/kg/day dose is not tolerated following a minimum of 1 week of treatment.

End of Study

The end of the study is defined as follows:

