		Screening/ Initial Visit	4 weeks	12 weeks	22 weeks	24 weeks	36 weeks	46 weeks	48 weeks	60 weeks	70 weeks	72 weeks		
Study Activity		76 weeks												
Study Days (±window)	-56- (-35) ±2	-28- (-7) ±2	1	28 (±5)	84 (±7)	154 (±7)	168 (±7)	252 (±7)	322 (±7)	336 (±7)	420 (±7)	490 (±7)	504 (±7)	532 (±7)
Clinic Visits	Visit S-1	Visit S-2	Visit 1a	Visit 2	Visit 3	Visit 4	Visit 5	Visit 6	Visit 7	Visit 8	Visit 9	Visit 10	11/EOT /Start of Optmnl Extension Period ¹¹	Visit 12 ^c
Fibroscan (where available)			X				X			X			X	
QoL questionnaire (PedsQL)			X				X			X			X	
Patient/Caregiver/Clinician Patient Global Impression of Change			X ¹¹	X	X		X			X			X	
Patient/Caregiver/Clinician Patient Global Impression of Symptoms				X	X	X	X	X	X	X	X	X	X	
Pregnancy test ¹¹	x ¹¹	X	x ¹¹	X	X	X	X	X	X	X	X	X	X	X
Telephone contact			Patients will be contacted via telephone for adverse event monitoring at Weeks 8, 18, 30, 42, 54, and 66											
Liver biopsy ¹¹													X	
Study drug dispensed ¹¹			X	X	X		X	X		X	X		X ¹¹	

Study Activity	Screening Period (Cohort 2 only)		Treatment Period										Follow-up Period ^h	
			Screening/ Inclusion Visit	4 weeks	12 weeks	22 weeks	24 weeks	36 weeks	46 weeks	48 weeks	60 weeks	70 weeks		
Study Days (\pm window)	-56- (-35) ± 2	-28- (-7) ± 2	1	28 (± 5)	84 (± 7)	154 (± 7)	168 (± 7)	252 (± 7)	322 (± 7)	336 (± 7)	420 (± 7)	490 (± 7)	504 (± 7)	532 (± 7)
Clinic Visits	Visit S-1	Visit S-2	Visit 1a	Visit 2	Visit 3	Visit 4	Visit 5	Visit 6	Visit 7	Visit 8	Visit 9	Visit 10	Visit 11/EOT /Start of Optional Extension Period ⁱ	Visit 12 ^c
Adverse events ^o p	Continuous collection													
Study drug compliance evaluated				X	xq		X	xq		X	X		xq	

eCRF: electronic case report form; eDiary: electronic diary; EOT: end of treatment; p-C4: plasma 7a Hydroxy 4-cholesten-3-one; PedsQL: pediatric quality of life; QoL: quality of life.

a For patients in Cohort I, Visit 1 coincides with Visit 9 in Study A4250-005. Assessments that have been performed at Visit 9 during Study A4250-005 will not be repeated.

b Assessments must also be performed at the time a patient is prematurely withdrawn from the study. If a patient discontinues prior to week 72, additional phone contact will be made every 3 months up to a total study participation of 72 weeks to assess if the patient has had biliary diversion or liver transplantation.

c Assessments must be performed 28 days following the final dose of study drug.

d Only for Cohort 1.

e Includes current medications.

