7.2.3 Withdrawal of Patients

Patients/caregivers will be informed that they have the right to withdraw from the study at any time, without prejudice to their medical care, and that they are not obliged to state their reasons.

Any withdrawal, and reasons for withdrawal, must be fully documented in the eCRF and source documents and the patient followed by the investigator/investigative staff. Withdrawn patients will not be replaced.

Patients will be withdrawn in the following circumstances:

- A patient's/caregiver's desire for withdrawal for any reason
- Lost to follow-up (every effort must be made to contact the patient/caregiver; a certified letter must be sent)
- An AE which, in the opinion of the investigator, necessitates withdrawal
- Death
- A patient's/caregiver's substantial non-compliance (eDiary and study drug compliance) or protocol violation
- An investigator's opinion that continuing the patient in the study is not appropriate. The investigator may withdraw a patient at any time, if it is considered to be in the patient's best interest
- Liver transplantation

The reason and the date the patient is withdrawn from the study will be documented in the eCRF and source documents. If a patient is withdrawn from further treatment with the study drug, the investigator/investigative staff will attempt to complete all Visit 11 procedures at the time the patient is prematurely withdrawn from the study. The investigator/investigative staff will also attempt to complete all Visit 12 procedures 28 days following premature withdrawal (i.e., 28 days following the final dose of the study drug).

If a patient discontinues prior to Week 72, additional telephone contacts will be made every 3 months after the Follow-up Visit (Visit 12) up to Week 72 to gather whether or not the patient has had biliary diversion or liver transplantation, and of ongoing TEAEs at the time of discontinuation have resolved. The telephone calls will take place up until 72 weeks even if the patient has biliary diversion or liver transplant.

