9.1.2 Secondary Efficacy Endpoints

EU and rest of world: Proportion of positive pruritus assessments at the patient level over the 72-week treatment period using the Albireo ObsRO instrument.

US: Change from baseline in serum bile acids after 72 weeks of treatment.

All Regions:

- Change from baseline in serum bile acids at Weeks 4, 12, 22, 24, 36, 46, 48, 60, 70, 72, and 76
- Proportion of individual assessments meeting the definition of a positive pruritus assessment at the patient level using the Albireo ObsRO instrument from Weeks 0-4, Weeks 0-12, Weeks 0-22, Weeks 0-24, Weeks 0-36, Weeks 0-46, Weeks 0-48, Weeks 0-60, and Weeks 0-70, respectively, or the proportion of positive pruritus assessments at each 4-week interval between Visit 1/Screening and Visit 5/Week 24, then by each visit between Visit 5/Week 24 to Visit 12/Week 76
- Proportion of individual AM assessments meeting the definition of a positive pruritus assessment at the patient level using the Albireo ObsRO instrument from Weeks 0-4, Weeks 0-12, Weeks 0-22, Weeks 0-24, Weeks 0-36, Weeks 0-46, Weeks 0-48, Weeks 0-60, Weeks 0-70, and Weeks 0-72, respectively, or the proportion of positive pruritus assessments at each 4-week interval between Visit 1/Screening and Visit 5/Week 24, then by each visit between Visit 5/Week 24 to Visit 12/Week 76
- Proportion of individual PM assessments meeting the definition of a positive pruritus assessment at the patient level using the Albireo ObsRO instrument from Weeks 0-4, Weeks 0-12, Weeks 0-22, Weeks 0-24, Weeks 0-36, Weeks 0-46, Weeks 0-48, Weeks 0-60, Weeks 0-70, and Weeks 0-72, respectively, or the proportion of positive pruritus assessments at each 4-week interval between Visit 1/Screening and Visit 5/Week 24, then by each visit between Visit 5/Week 24 to Visit 12/Week 76
- All-cause mortality, number of patients undergoing biliary diversion surgery or liver transplantation. These parameters will be evaluated separately and together at weeks 24, 48, and 72

- Change in growth from baseline to Weeks 24, 48, and 72 after initiation of A4250 treatment, defined as the linear growth deficit (height/length for age, weight for age, mid-arm circumference, and body mass index [BMI]) compared to the standard growth curve (Z-score, standard deviation [SD] from P50)
- Change in AST to platelet ratio index (APRI) score and Fib-4 score from baseline to Week 72

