10.1.3 Recording and Reporting of Serious Adverse Events

Every SAE (regardless of severity and causality) that occurs once the caregiver/patient has signed the ICF and until the post-treatment follow-up (Visit 12), and 28 days after the final dose of study drug, should immediately and not later than within 24 hours of knowledge of the event, be reported by the investigator or delegate in the SAE Report Form.

Report of a SAE must include at least the following information:

- Patient identification information (study number, site number, initials, and date of birth [as per local country requirements for data protection])
- The last study drug administration date
- The diagnosis of the event with the description (or a brief description of signs/symptoms/clinical course if the diagnosis is not available) and the date of onset
- The action used to treat the event (i.e., treatment medications, temporary discontinuation)
- The reason(s) for considering the event serious
- The relationship of the event to the study drug or to the study procedure (e.g., the investigator's assessment of causality)
- A brief narrative of the SAE

Follow-up reports including all new information obtained of the subsequent course of the SAE must be prepared and the information collected in the SAE Report Form submitted to ICON

DRUG SAFETY (Pharmacovigilance and Safety Services Department) by e-mail within 24 hours of knowledge of the event.

The pharmacovigilance manager (PVM) may contact the investigator to obtain further information on a reported SAE. The investigator/investigative staff must respond to any request for follow-up information or answers to questions regarding the SAE within the same timelines as for initial reports.

The PVM reports the occurrence of the SAE and follow-up to the Albireo Medical Monitor for medical assessment of the case.

Should an outcome of death occur within the study period or within 28 days after the last administration of study drug, an SAE Report Form should be completed including the main and contributory causes of death.

All SAE reports must be e-mailed to the following e-mail address within **24 hours**:

ICON DRUG SAFETY (Pharmacovigilance and Safety Services Department)

E-mail: PPD

If email is unavailable, SAEs may be transmitted via fax to the following number:

Fax No.: PPD

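### Section 10.1.2 contradicts its own 28-day AE window for patients who stop early, and the calls to Week 72 do not ask about death, so late deaths could be missed

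*Protocol*

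**What the plan says.** On AE recording, Section 10.1.2 collects every AE, serious or not, from consent "until the post-treatment follow-up (Visit 12), 28 days after the last dose of study drug". Two paragraphs later, after a sentence on telephone follow-up of ongoing TEAEs to Week 72, it says: "No new AEs will be recorded after the patient has permanently discontinued study drug". Section 10.1.3 requires SAE reporting "until the post-treatment follow-up (Visit 12), and 28 days after the final dose of study drug". Section 7.1.1 says of Visit 12: "All patients prematurely withdrawn will have this visit 28 days after the last dose of study drug for AE and other follow-up". Section 7.1.3.4 lists AE monitoring at that visit and names premature withdrawals among those who attend. Table 1 footnote o ends AE collection at study discontinuation.

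On the calls, patients who stop before Week 72 are telephoned every three months after Visit 12. Section 7.2.3 gives the purpose: "to gather whether or not the patient has had biliary diversion or liver transplantation, and of ongoing TEAEs at the time of discontinuation have resolved". Section 7.1.1 has the same content. Table 1 footnote b names only diversion and transplantation, and says that "additional phone contact will be made every 3 months up to a total study participation of 72 weeks".

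On the endpoint, Section 9.1.2 lists "All-cause mortality, number of patients undergoing biliary diversion surgery or liver transplantation", to be evaluated separately and together at Weeks 24, 48 and 72. Section 11.2.2.6 compares the upper 95% limit for the proportion with diversion, transplantation or death with the proportion expected from the untreated reference cohort.

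**The concern.** There are two linked gaps.

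First, the stop on new AEs is tied to permanent discontinuation of drug, whereas the collection window is tied to Visit 12. A site that follows the stop literally would record no new event between last dose and Visit 12 in a patient who leaves early. Section 10.2.2.8 has patients who stopped for certain safety reasons monitored weekly after discontinuation. Under the same literal reading, a new event found there would also go unrecorded.

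Second, after Visit 12 the calls are the only scheduled contact. They name two of the three components of the composite and omit the third, which is also a secondary endpoint in its own right. A death that is not asked about can only lower the A4250 event count, so any resulting error in the comparison with the reference cohort would favour A4250.

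**Working it through.** **1. AE recording between last dose and Visit 12, for an early discontinuer**

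| Place | New AE recorded in these 28 days? |
|---|---|
| 10.1.2, collection window | Yes |
| 10.1.3, SAE window | Yes, if serious |
| 7.1.1 and 7.1.3.4, Visit 12 | Yes, AE follow-up is listed |
| 10.1.2, later sentence | No |
| Table 1 footnote o | Depends on when study discontinuation is dated |

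The first and fourth rows cannot both be followed.

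**2. Which outcomes are exposed after Visit 12**

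- Diversion and transplantation: asked about to Week 72 in 7.1.1, 7.2.3 and footnote b. Not exposed.
- Death within 28 days of last dose: an SAE form is required by 10.1.3. Not exposed.
- Death from day 28 to Week 72: not in the call content. 10.1.3 also requires a form for a death within the study period, but that term is not defined for the call phase, and 10.1.2 bars new AEs there. Exposed.
- For the composite, a late death matters only if the patient had no earlier diversion or transplant; otherwise the patient already counts. For mortality evaluated separately every late death matters, including deaths after transplantation, which is itself a withdrawal reason in 7.2.3.

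**3. Length of the exposed interval**

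With last dose at week w, Visit 12 falls at w + 4, so the interval is 72 − (w + 4) = 68 − w weeks. For w = 24 it is 44 weeks; for w = 48 it is 20 weeks. The maximum, for a patient stopping at about Day 1, is 68 weeks.

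**4. The protocol's own power figure**

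Inputs from Section 11.1: 30% expected untreated, 10% on A4250, one-sided alpha 2.5%, n = 48 to 60, success if the upper limit is below 30%; stated power about 89% to 96%.

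Exact (Clopper-Pearson) upper limit for x events in n: U(x, n) = the 0.975 quantile of Beta(x + 1, n − x).

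- n = 48: U(7) = 27.8%, U(8) = 30.2%. At most 7 events are allowed; P(X ≤ 7 | 48, 0.10) = 89.8%.
- n = 60: U(10) = 28.5%, U(11) = 30.4%. At most 10 events are allowed; P(X ≤ 10 | 60, 0.10) = 96.6%.

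This reproduces the stated figures. The Wilson interval (95.4% and 98.5%) and the Wald interval (98.1% and 98.5%) do not.

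**5. Sensitivity to missed deaths**

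- At the boundary, one missed death reverses the result: 8 to 7 of 48, or 11 to 10 of 60.
- At the protocol's example (10% of 60 = 6 events) it does not: U(6) = 20.5%, U(5) = 18.4%, U(4) = 16.2%, all below 30%.
- Assumption: a fixed share of all composite events is missed. With a true rate of 30%, the chance that the upper limit falls below 30% is:

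| Share missed | n = 48 | n = 60 |
|---|---|---|
| 0% | 1.1% | 1.4% |
| 5% | 1.9% | 2.5% |
| 10% | 3.2% | 4.4% |
| 20% | 8.2% | 11.7% |

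Only late deaths without an earlier event can be missed, so the larger shares would require such deaths to be a sizeable part of all events. The protocol gives neither a discontinuation rate nor a rate of death after discontinuation, so no row can be chosen as the expected one.

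**The case against.** The best defence on AEs is context. The disputed sentence directly follows one about the telephone calls and may be meant only for the phase after Visit 12. Sections 7.1.1, 7.1.3.4 and 10.1.3 all support that intent. It is a plausible reading, but the trigger written down is permanent discontinuation of drug, not Visit 12. The contradiction in the text stands; a wholesale loss of the 28-day window in practice is not established.

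On deaths, the 10.1.3 rule covers the study period as an alternative to the 28 days, and footnote b describes the calls as part of study participation. Section 11.2.2.2 asks for efficacy data after discontinuation as far as possible. Section 7.1.3 makes vital status part of the minimum contact for any study visit, which reaches Visit 12. A call about transplantation would also ordinarily reveal a death. All of this lowers the risk. None of it obliges the caller to establish vital status or a date of death after Visit 12.

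A reader might infer that all three components are under-counted. The documents do not support that, because diversion and transplantation are collected to Week 72. Nor do they show that early discontinuers are mainly patients with toxicity: the withdrawal reasons in 7.2.3 include caregiver wish, non-compliance, loss to follow-up and transplantation.

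It is also fair to say that Section 11.1 disclaims formal hypothesis testing and that the 30% is only an example.

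**Conclusion.** Two things are established from the text. Section 10.1.2 contradicts itself on AE recording in the 28 days after last dose, with footnote o adding a further stop point. The call content omits death although mortality is an endpoint to Week 72.

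What follows for the endpoint is a risk, not a demonstrated under-count. It is confined to deaths between day 28 after the last dose and Week 72 and, for the composite, to patients with no earlier diversion or transplant. Its direction is known: any error would favour A4250. Its size cannot be estimated from the protocol. The boundary results rest on the exact interval, which the protocol does not name but which matches its stated power, and on the illustrative 30%. The table of missed shares is an assumption, not a forecast.

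**What to change.** - In 10.1.2, tie the stop on new AEs to Visit 12 (28 days after the last dose) instead of to permanent discontinuation of study drug, and align Table 1 footnote o with it.
- In 7.1.1, 7.2.3 and Table 1 footnote b, add vital status, with date and cause of death, to the three-monthly calls.
- In 10.1.3, state that the study period in the death-reporting rule includes the call phase to Week 72.

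The cost is a few sentences and one more question in calls already scheduled. No stated sample size or power figure changes. Collecting related SAEs after Visit 12 would be a new rule and is not needed to resolve the conflict.

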
h Itching, scratching, and sleep will be assessed via an eDiary (issued with any necessary training to patients/caregivers at Visit 1). Patients/caregivers will be instructed to fill in the eDiary every morning and evening for the first 24 weeks and the last 21 days before all the remaining visits to the clinic. There will be no interruption between Visits 11 and 12. Patients participating in the extension period will stop eDiary entries at Visit 11. See Table 4 for detailed parameters.
 
j Patients will fast (only water intake is permissible) for at least 4 hours prior to the collection of samples for serum bile acids and vitamin A. Exceptions can be made for infants, less than 12 months of age, if unable to fast for the entire 4 hours.
 
k Autotaxin and p-C4 samples will not be collected for patients ≤ 10 kg. For girls who have reached menarche. Serum test will be performed at Visit S-1 for Cohort 2 only and Visit 1 (for Cohort 1 only); urine test will be performed at all other visits. If a urine pregnancy test is positive, a serum pregnancy test should be performed to confirm the pregnancy.
 
m If a liver biopsy is performed at any time during A4250-008 according to the local regulations or standard of care, the biopsy results should be recorded in the eCRF. If the patient has liver biopsy results collected in study A4250-005 or prior to Week 24 in study A4250-008, the patient will be asked to consent to a follow up liver biopsy, if allowed per local regulations, at Visit 11 unless 2 prior liver biopsy results have been collected with at least 1 year between biopsies. Liver biopsies will not be performed in Spain.
 
n Study drug will be taken once daily from Day 1 through Day 504 as described in Section 8.2.
 
o Adverse event information will be collected from the time of signing of the informed consent form to study discontinuation.
 
p For hepatic adverse events and/or hepatic decompensation, a PK sample should be collected as close to the onset of the event as possible (PK samples not required during screening period).
 
q Dosage form acceptability questions will be asked of the caregiver and/or patient at Visits 3, 6, and 11.
														

Study Activity	Screening Period (Cohort 2 only)		Treatment Period										Follow-up Period ^u	
			Screening/ Inclusion Visit	4 weeks	12 weeks	22 weeks	24 weeks	36 weeks	46 weeks	48 weeks	60 weeks	70 weeks	72 weeks	

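### Section 10.1.2 collects AEs for 28 days after the last dose, then bars new AEs from permanent discontinuation, without limiting the bar to the period after Visit 12

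*Protocol*

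**What the plan says.** Section 10.1.2 (Recording of Adverse Events) gives two end points for new AEs.

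- Its second paragraph collects serious and non-serious AEs from consent "until the post-treatment follow-up (Visit 12), 28 days after the last dose of study drug", and keeps collection going through the optional extension.
- Its fourth paragraph has two sentences. The first follows TEAEs that are ongoing at discontinuation by 3-monthly telephone calls to Week 72. The second reads "No new AEs will be recorded after the patient has permanently discontinued study drug".

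Other sections bear on the same window.

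- Section 10.1.3 requires SAEs to be reported "until the post-treatment follow-up (Visit 12), and 28 days after the final dose of study drug". It also requires a report form "Should an outcome of death occur within the study period or within 28 days after the last administration of study drug".
- Section 7.1.1, on Visit 12: "All patients prematurely withdrawn will have this visit 28 days after the last dose of study drug", with AE follow-up named as a purpose.
- Section 7.2.3: site staff "will also attempt to complete all Visit 12 procedures 28 days following premature withdrawal".
- Section 7.1.3.4 lists AE monitoring among the Visit 12 procedures and covers patients who withdraw early.
- Table 1 footnote c, on Visit 12: "Assessments must be performed 28 days following the final dose of study drug".
- Table 1 footnote o, on the AE row: "Adverse event information will be collected from the time of signing of the informed consent form to study discontinuation".

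**The concern.** The two sentences of 10.1.2 cannot both be followed as written. A patient who stops drug for good before Week 72 is due a Visit 12 with AE monitoring 28 days after the last dose. The bar on new AEs starts the moment that patient stops. Site staff who apply the bar literally would hold the visit and record no new event at it.

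Long-term safety and tolerability is the first secondary objective (6.2), and TEAE incidence is the primary safety analysis (section 10). The TEAE definition in 10.1.2 counts events from the first dose and does not exclude those that begin shortly after the last dose. Up to 50 sites are planned. If some apply the bar and others apply the 28-day rule, AE counts after discontinuation will differ by site for reasons unrelated to the drug. An event that was never recorded cannot be recovered at analysis.

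**Working it through.** There is no power or sample-size figure to reproduce. The check compares the texts, with one subtraction.

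**Length of the window.** Table 1 puts Visit 11 on Day 504 and Visit 12 on Day 532: 532 − 504 = 28 days. This agrees with the 28 days in 10.1.2, 10.1.3, 7.1.1 and 7.2.3.

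**Last point for recording a new AE in a patient who stops drug before Week 72:**

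| Source | Days after last dose |
|---|---|
| 10.1.2, second paragraph | 28 |
| 10.1.3 (SAEs, deaths) | 28 |
| 7.1.1, 7.1.3.4, 7.2.3 (Visit 12) | 28 |
| 10.1.2, fourth paragraph, second sentence | 0 |
| Table 1 footnote o | unclear: study discontinuation is not tied to the last dose or to Visit 12 |

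The difference inside 10.1.2 is 28 − 0 = 28 days, which is the whole post-dose window.

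**What the bar was probably meant to cover.** It shares a paragraph with the 3-monthly calls. Sections 7.1.1 and 7.2.3 place those calls after Visit 12. They limit them to whether the patient has had biliary diversion or transplantation and whether TEAEs ongoing at discontinuation have resolved. A rule against opening new AEs at those calls fits this purpose and would start on day 28. The sentence as printed starts on day 0.

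**Which events are exposed.** SAEs and deaths stay reportable to 28 days under 10.1.3, so the literal bar mainly costs new non-serious AEs. An SAE is by definition also an AE, and 10.1.2 sends AEs to the eCRF. A strict reader could therefore put a post-dose SAE on the SAE form and leave it out of the eCRF.

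**Extension patients.** Three places give their rule.

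- 7.1.1 says that the 4-week follow-up is dropped for patients who continue. A separate sentence gives withdrawal during the extension its own end-of-treatment assessments.
- 7.1.3.6 asks for that visit at once when a patient withdraws.
- Table 2 has two columns, 16-weekly visits and end of treatment, so 0 contacts are scheduled afterwards.

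The 28-day SAE and death window in 10.1.3 has no extension exception, and its 24-hour reporting clock runs from knowledge of the event. Patients stopped for safety reasons are monitored weekly under 10.2.2.8: 28 / 7 = at most 4 contacts in the window, fewer if values normalize sooner. Other withdrawals have none scheduled.

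**The case against.** The strongest reply is that context already settles the meaning. The bar follows directly on the telephone-call sentence, and the literal reading would contradict the same section, the SAE window and the AE monitoring listed at Visit 12. Staff who hold a scheduled visit with that item on the list are unlikely to record nothing. This stands as evidence of intent, and it makes the literal reading the less likely one. It does not supply the missing limit. The printed trigger is stopping drug, the calls start only after Visit 12, and footnote o gives a further end point that does not decide between them.

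A reader might also infer that the extension schedule contradicts 7.1.1 and 7.2.3 by leaving out a 28-day visit which those sections promise to every withdrawn patient. The documents do not support that.

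- Section 7.1.1 separates the two cases: premature withdrawal from the study leads to Visit 11 assessments, and withdrawal during the extension leads to the extension end-of-treatment visit.
- Section 7.2.3 pairs Visit 12 with completing Visit 11 procedures at withdrawal, which an extension patient has already passed.
- The Visit 12 paragraph of 7.1.1 opens with patients outside the extension, and 7.1.3.4 is headed the same way.
- Footnote c belongs to Table 1 and does not govern Table 2.

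Omitting the visit is therefore a design decision, and a sensible one for patients who move straight to commercial drug. What remains is that the 10.1.3 duty applies to extension patients with no scheduled contact to support it after the end-of-treatment visit.

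**Conclusion.** The contradiction within 10.1.2 is real and worth correcting. Its size is 28 days of new-AE collection against 0 for a patient who permanently discontinues. The consequence depends on some sites following the bar literally; if all read it as limited to the later calls, nothing is lost. The exposed data are mainly new non-serious AEs in that window, and no efficacy analysis changes. The protocol does not give the number of patients who will discontinue, so no count of missed events is offered.

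The lack of a 28-day contact in the extension is not an error in the plan. It is a place where a small addition would help sites meet a reporting duty they already have.

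**What to change.** **Correction.** Replace the bar in 10.1.2 with text such as: *New AEs are not recorded after Visit 12 (28 days after the last dose); at the later 3-monthly telephone calls, only TEAEs already ongoing at discontinuation are followed.* Keep the existing sentence that continues AE collection through the extension. Align Table 1 footnote o to the same end point. The cost is wording in two places, with no added visit or blood draw.

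**Optional.** Add to 7.1.3.6 and Table 2 one telephone safety contact 28 days after the last dose for extension patients who do not move to commercial drug, and name it beside Visit 12 in 10.1.2 and 10.1.3. The cost is that wording and one call per such patient; the protocol does not give their number.
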